6.0 Data and Specimen Banking

- 6.1 Storage and Access: All study data will be stored on excel spreadsheets stored in Box. Only the PI and members of the research team will have access to the data.
- 6.2 Data: The data from this study will be collected both from Epic and directly from the patient. The data collected includes: demographic data, age, weight, ASA class, duration of surgery, length of stay in recovery room both phase 1 and 2, time to place LMA, number of attempts, ease of LMA insertion, blood staining, sore throat prior to discharge and at 24 hours post surgically, and any adverse events.

7.0 Sharing of Results with Participants

- 7.1 Study results will not be shared with participants. De-identified study data may be shared with the peer-reviewed journal.

8.0 Study Population

- 8.1 Inclusion Criteria: Adult patients aged 18-80 undergoing outpatient ambulatory surgery under general anesthesia that is amenable to LMA.
- 8.2 Exclusion Criteria: Patients under the age of 18, non-English speaking patients, patients with abnormal airway anatomy
- 8.3 Screening: Patients will be screened by looking at the surgical schedule. They will be contacted by the research team ahead of time and have the study introduced on the morning of surgery. They will have adequate time to evaluate the study and read through the consent and ask questions.

9.0 Vulnerable Populations

- 9.1 Vulnerable Populations:

Population / Group	
Children	Excluded from Participation

PROTOCOL TITLE: Comparison of Ambu Auragain and I-Gel Supraglottic Airways in

Adult Patients at an Ambulatory Surgery Center

VERSION DATE: 4/3/2021

Pregnant women/fetuses/neonates	Excluded from Participation
Prisoners	Excluded from Participation
Adults lacking capacity to consent and/or adults with diminished capacity to consent, including, but not limited to, those with acute medical conditions, psychiatric disorders, neurologic disorders, developmental disorders, and behavioral disorders	Excluded from Participation
Non-English speakers	Excluded from Participation
Those unable to read (illiterate)	Excluded from Participation
Employees of the researcher	Excluded from Participation
Students of the researcher	Excluded from Participation
Undervalued or disenfranchised social group	Excluded from Participation
Active members of the military (service members), DoD personnel (including civilian employees)	Excluded from Participation
Individual or group that is approached for participation in research during a stressful situation such as emergency room setting, childbirth (labor), etc.	Excluded from Participation
Individual or group that is disadvantaged in the distribution of social goods and services such as income, housing, or healthcare.	Excluded from Participation
Individual or group with a serious health condition for which there are no satisfactory standard treatments.	Excluded from Participation
Individual or group with a fear of negative consequences for not participating in the research (e.g. institutionalization, deportation, disclosure of stigmatizing behavior).	Excluded from Participation
Any other circumstance/dynamic that could increase vulnerability to coercion or exploitation that might influence	Excluded from Participation

PROTOCOL TITLE: Comparison of Ambu Auragain and I-Gel Supraglottic Airways in Adult Patients at an Ambulatory Surgery Center

VERSION DATE: 4/3/2021

consent to research or decision to continue in research.	
---	--

9.2 Additional safeguards: N/A

10.0 Local Number of Participants

10.1 Local Number of Participants to be Consented: 165

11.0 Local Recruitment Methods

11.1 Recruitment Process: Patients will be recruited from the group of adult patients undergoing surgery at the University of Minnesota Ambulatory Surgery Center. On the day of surgery as soon as they are checked in, patients will be informed of a research opportunity by a member of the clinical care staff, including the check-in staff, nursing staff, or member of the anesthesiology team, and asked if they are interested in talking with a member of the research team. A research team member will then explain the study and present the consent form. All patients will have sufficient time to review the consent and ask questions and go over the potential risks of the study with the research team as they arrive several hours prior to the procedure. If they decide to participate they will be consented and given a copy of the consent form for their records.

11.2 Identification of Potential Participants: Patients will be identified by members of the research team by evaluating the surgical schedule. Patients who have opted out of research will not be approached. Patients who agree to participate will sign a consent and HIPAA authorization form.

11.3 Recruitment Materials: N/A

11.4 Payment: No payment will be provided to patients.

12.0 Withdrawal of Participants

12.1 Withdrawal Circumstances: Subjects who have consented and for some reason choose not to participate will be withdrawn and a notation will be made in the study records and these people will be considered screen failures. The surgeon may choose to withdraw the patient from the study prior to surgery for any medical reason or if they suffer a major life-threatening adverse event.

12.2 Withdrawal Procedures: If the patient is withdrawn from study prior to the procedure, they will be noted in study records as screen failures. If they undergo the procedure and they decide they no longer want to be a part of the study or withdrawn by the physician, they will be withdrawn and no further data will be collected. This will also be noted in the study documentation.

PROTOCOL TITLE: Comparison of Ambu Auragain and I-Gel Supraglottic Airways in Adult Patients at an Ambulatory Surgery Center

VERSION DATE: 4/3/2021

12.3 Termination Procedures: If the study is terminated for any reason, or there are more than 5% major adverse events the data that is already collected will be stored in a secure location only accessible to research personnel on this study. No further data will be collected if the study is terminated.

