3.0 Study Endpoints/Events/Outcomes

- 3.1** Primary Endpoint/Event/Outcome: OLP immediately after placement
- 3.2** Secondary Endpoint(s)/Event(s)/Outcome(s): Time to placement, insertion attempts, first attempt success rate, ease of insertion, number of mid case adjustments, sore throat upon discharge from recovery room and at 24 hours after surgery analyzed using NRS 0-10 scale, and blood staining of LMA.

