5.2 Study Procedures: Patients will be approached on the day of surgery about participating in the trial. This will be done as soon as they arrive at the ASC to allow adequate time for them to review the study procedures and consent forms. All questions will be answered and patients will be ensured that they have adequate time to review and understand all study procedures. Patients undergoing all surgical procedures with general anesthesia appropriate for an LMA will be eligible to participate. Once enrolled patients will be randomized to one of two groups. Patients in group 1 will receive an I-gel LMA. Those in group 2 will receive an Ambu Auragain LMA. A standard anesthetic induction will take place using propofol, lidocaine, dexamethasone, and ondansetron. The LMA will be placed by an experienced anesthesia provider. Once absence of lid reflex is confirmed, the LMA will be placed according to instructions from the LMA such that the patient is supine with head in sniffing position. A water-based lubricant will be used on the LMA to ease insertion. The ambu auragain will be inflated to a pressure of 60cmH20. Muscle relaxant will not be used in any patient and maintenance of anesthesia will be with propofol infusion. A research assistant or another anesthesia provider will be in the room to capture all data points. OLP will be measured immediately after insertion. This will be accomplished by closing the expiratory valve while keeping fresh gas flow at 3 liters/minute until equilibrium is reached. Once in the recovery room the patient will be asked about a sore throat immediately prior to discharge. Patient will also be called 24 hours after surgery to evaluate sore throat analyzed using NRS 0-10 scale.

Baseline demographics such as surgical procedure, intraoperative opioids, surgical procedure length, BMI, weight, age, and sex will be recorded.

PROTOCOL TITLE: Comparison of Ambu Auragain and I-Gel Supraglottic Airways in Adult Patients at an Ambulatory Surgery Center

VERSION DATE: 4/3/2021

- 5.3 Study Duration: Once ready to discharge from PACU the patient will end study participation with one follow up call on the day after surgery. The study should take 1 month to enroll and another 2 months for study analysis.
- 5.4 Individually Identifiable Health Information: This study does involve PHI, please see combined consent/HIPAA form.
- 5.5 Use of radiation: N/A
- 5.6 Use of Center for Magnetic Resonance Research: N/A

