23.0 Resources Available

23.1 Resources Available: Research assistants are available to aid in consent and data acquisition. All research assistants will be familiar with the study protocol and have experience working with similar studies.

We plan to enroll 148 patients and consent 165, assuming around 10% drop out. This center performs approximately 100 surgical procedures weekly.

We plan to conduct this study over 4 weeks. Enrollment and data collection will be completed at this time. Statistical Analysis will take approximately one month to complete.

All procedures will be performed in the clinical facilities at the MHealth Clinics and Surgery Center. Data storage and analysis will be done using desktop equipment which is available at the Research Office B573 Mayo.

In the event that this research activity results in an injury, treatment will be available, including first aid, emergency treatment and follow-up care as needed. Care for such injuries will be billed in the ordinary manner, to the patient and/or insurance company. All study personnel will be adequately trained by the Principle Investigator on the study protocol and study conduct. A log will be maintained to track which personnel are trained. A delegation of authority log will also be maintained to track which personnel are responsible for specific duties.

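### Section 12.3 ends all study data collection when the study is terminated, with no exception for patients who have already received a device

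*Combined protocol and SAP*

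**What the plan says.** Section 12.3 opens with two situations: "If the study is terminated for any reason, or there are more than 5% major adverse events". In either case, data in hand are to be stored securely. The section then ends with "No further data will be collected if the study is terminated".

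Other sections define what is still due from a patient after the device has been placed:

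- Section 3.2 lists as a secondary endpoint "sore throat upon discharge from recovery room and at 24 hours after surgery analyzed using NRS 0-10 scale".
- Section 5.2 makes the later assessment a procedure: "Patient will also be called 24 hours after surgery to evaluate sore throat analyzed using NRS 0-10 scale".
- Section 5.3 says that after the recovery room "the patient will end study participation with one follow up call on the day after surgery".
- Section 6.2 counts among the study data "sore throat prior to discharge and at 24 hours post surgically, and any adverse events".

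Section 12.2 has a similar rule for individuals. If a patient leaves, or a physician withdraws the patient, after the procedure, collection stops for that patient.

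**The concern.** This point is about closing the whole study, not about one patient leaving. Patients affected by 12.3 have consented, have been exposed to a device and have not asked to stop. A site that follows the sentence to the letter would not ask about sore throat in patients still in recovery, would not make the outstanding 24-hour calls, and would not enter the outcome of an adverse event that had not yet resolved.

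Two separate things are at stake. One is a few values of a secondary endpoint. The other is the study record of any event still open. The second matters most if the termination was for safety, because the Data and Safety Monitoring Committee would then have to give its advice on a record that stops at the moment of closure. Losing data here serves no purpose that the protocol states.

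**Working it through.** **Step 1. Is there an exception anywhere?** The sections that could contain one read as follows.

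| Section | Content | Exempts exposed patients from 12.3? |
|---|---|---|
| 5.2, 5.3 | Recovery-room question and next-day call | No; termination is not mentioned |
| 6.2 | Adverse events are study data | No; this places them under the stop |
| 12.1, 12.2 | Withdrawal of individuals | No; 12.2 also ends collection |
| 17.2 | Weekly review by the investigator and staff, monthly data to the committee | No; nothing on follow-up after termination |
| 19.1, repeated in 23.1 | Treatment and follow-up care for research injury | No; covers care and billing, not recording |

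The rule therefore stands without exception.

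**Step 2. Inputs for the size.** Section 23.1: "We plan to enroll 148 patients and consent 165, assuming around 10% drop out". The same section gives 4 weeks for the study. Two assumptions are added because the protocol is silent: five operating days a week, and even accrual.

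**Step 3. The plan's own figures.** The 148 in the 15.2 table reproduces exactly with a Welch noncentral-t calculation (difference 3 cmH₂O, SDs 4.00 and 8.20, 80% power, two-sided alpha of 0.05 assumed because none is stated). The number to consent also reproduces: 148 / (1 − 0.10) = 164.4, rounded up to 165. Neither figure is in dispute.

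**Step 4. Patients inside the 24-hour window.**

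- With 148 patients: 148 / 4 = 37 a week, and 37 / 5 = 7.4 per operating day.
- With 165 patients: 165 / 4 = 41.25 a week, and 41.25 / 5 = 8.25 per operating day.

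A termination at the end of an operating day would thus catch about 7 to 8 patients before their call. Any still in recovery are among them.

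**Step 5. Share of the 24-hour data lost, by when the stop comes.**

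| Patients treated at the stop | 7 lost | 8 lost |
|---|---|---|
| 40 | 7/40 = 17.5% | 8/40 = 20.0% |
| 74 | 7/74 = 9.5% | 8/74 = 10.8% |
| 148 | 7/148 = 4.7% | 8/148 = 5.4% |

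The number lost is fixed by the daily pace, so the share falls as the study fills. If operating had paused before the termination, fewer patients would be affected.

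**Step 6. Open events.** The documents give no event rate and no time to resolution, so this number cannot be estimated. It may be zero.

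**The case against.** The case against is that little is lost. Follow-up lasts one day. The primary endpoint is leak pressure immediately after placement, so it is already in hand for anyone whose pressure has been measured. Injury care continues under 19.1, and since 6.2 draws part of the data from the electronic health record, an event may well be documented clinically. All of this stands, and it limits the point to study data, a secondary endpoint and the study's own event record. It does not remove the rule. Neither 19.1 nor 23.1 requires an outcome to be entered in the study record or sent to the committee.

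It can also be said that the sentence was meant only to stop enrolment. That may be so, but it says data, and a site can act only on what is written.

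Several stronger readings are tempting, and the documents do not support them:

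- *That 5% major adverse events is an operating stopping rule.* Section 12.3 joins that condition to termination with an 'or' and never says that it causes termination. It defines neither the denominator nor what counts as major. The point does not need it, since termination for any reason includes a safety termination.
- *That two or three open events would go unrecorded.* If the denominator is patients treated so far, exceeding 5% takes 2 events at 20 to 39 patients (2/39 = 5.1%) and 3 at 40 to 59 (3/59 = 5.1%). Those are cumulative counts. Earlier events may have resolved and been recorded.
- *That the missing calls would bias the device comparison.* The cut-off would apply to both arms at once under 1:1 randomisation in small blocks (5.1). No mechanism favouring one arm is evident.
- *That the 24-hour call is a safety contact.* Section 5.2 describes it as a sore-throat assessment and does not say that adverse events are asked about.

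**Conclusion.** The point holds as a defect in a stated rule. On termination, 12.3 stops the planned assessments and the recording of event outcomes for patients who have already been exposed, and nothing elsewhere restores them. Certainty about the wording is high. The size is modest and conditional: nothing is lost unless the study closes early. If it does, about 7 to 8 patients lose sore-throat data, between roughly 5% and 20% of the 24-hour values depending on whether the stop comes late or at about 40 patients. An unknown number of open events, possibly none, would have no outcome in the study record. These figures rest on the planned 4 weeks, five operating days a week, even accrual and treatment continuing up to the stop.

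It would go too far to infer that patients would be left without care, or that the primary comparison is threatened. The change is worth making because it is cheap and because the gap would matter most at a safety termination.

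**What to change.** Replace the last sentence of 12.3 with wording such as:

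> On termination, no further patients are randomised. Patients who have already received a study device complete the planned recovery-room and 24-hour assessments, and the outcome of any adverse event open at termination is recorded and sent to the Data and Safety Monitoring Committee, unless the patient withdraws consent.

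Reconcile 12.2 with this text. Section 12.1 lets the surgeon withdraw a patient who has a major life-threatening event, and 12.2 then ends data collection if the withdrawal follows the procedure. Changing 12.3 alone could therefore still lose the events behind a safety termination. Section 12.2 should say that withdrawal by a physician after the procedure does not by itself end the recording of adverse-event outcomes. A patient's own withdrawal of consent would still be respected.

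The cost is an amendment to two short subsections, about one operating day of calls that are already planned, and brief recording of any open events. The change concerns only what is recorded and leaves the clinical care of patients as it is.

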13.0 Risks to Participants

13.1 Foreseeable Risks: This study has the following risks: None as both are FDA approved LMA devices and routinely used in clinical practice.

13.2 Reproduction Risks: N/A

13.3 Risks to Others: N/A

14.0 Potential Benefits to Participants

14.1 Potential Benefits: None.

15.0 Statistical Considerations

15.1 Data Analysis Plan: We plan to collect our data using excel which will be maintained in the box. When the study is completed and ready for statistical analysis the data will be shared with our staff statistician.

15.2 Power Analysis: Previous studies on OLP have shown that there was a mean difference between i-gel and AuraGain in OLP immediately after insertion in pediatrics of -5.9 cmH₂O (95% CI: -8.5 to -3.3) [Mihara EJA 2019 with estimated SD of 4.00 for AuraGel and 8.20 for i-gel] or an estimated mean difference of -1.8 cmH₂O (95% CI: -3.6 to 0.01) [Sabuncu SMJ 2018 with estimate SD of 3.56 for AuraGel and 4.20 for i-gel]. The table below shows the total sample size needed based upon the reported standard deviations from each study to detect a difference of at least 3 cmH₂O in OLP between AuraGel and i-gel:

Power	AuraGel SD	i-gel SD	Total Sample Size
80%	3.56	4.20	56
	4.00	8.20	148
90%	3.56	4.20	74
	4.00	8.20	198

15.3 Statistical Analysis: This study data will be de-identified and shared with our staff biostatistician to be analyzed. The statistician will be provided the protocol so they are able to analyze for primary and secondary objectives.

Continuous data will be summarized with mean (standard deviation) or median (interquartile range) and categorical data will be summarized by

PROTOCOL TITLE: Comparison of Ambu Auragain and I-Gel Supraglottic Airways in Adult Patients at an Ambulatory Surgery Center

VERSION DATE: 4/3/2021

count (percent). Normality will be evaluated with both the Shapiro-Wilk test and graphical evaluation. Univariate comparisons between groups will use t-tests or Mann-Whitney U-tests, as appropriate for normality, to compare continuous variables and chi-squared or Fisher's exact tests to compare categorical variables between groups. Linear regression models will be explored to adjust for variables that are imbalanced after randomization or other covariates that may be clinically relevant.

15.4 Data Integrity: All patients will be assigned a unique patient identifier. The data that will be sent to the statistician will be de-identified.

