5.0 Procedures Involved

- 5.1** Study Design: This is a level I randomized prospective outcomes study comparing two groups of patients. All patients scheduled for general anesthesia at the M Health Ambulatory Surgery Center who are appropriate for an LMA will be approached for the study. Once enrolled patients will be randomized 1:1 between the groups based on a randomization schedule generated before study initiation using permuted

PROTOCOL TITLE: Comparison of Ambu Auragain and I-Gel Supraglottic Airways in Adult Patients at an Ambulatory Surgery Center

VERSION DATE: 4/3/2021

block randomization with blocks of sizes 2, 4, and 6 used in equal proportion (i.e., 1:1:1) to ensure approximate balance at any point in the study between the two groups. Patients in group 1 will receive an I-gel LMA. Those in group 2 will receive an Ambu Auragain LMA. A standard anesthetic induction will take place using propofol, lidocaine, dexamethasone, and ondansetron. The LMA will be placed by an experienced anesthesia provider. Once absence of lid reflex is confirmed, the LMA will be placed according to instructions from the LMA such that the patient is supine with head in sniffing position. A water-based lubricant will be used on the LMA to ease insertion. The ambu auragain will be inflated to a pressure of 60cmH20. Muscle relaxant will not be used in any patient and maintenance of anesthesia will be with propofol infusion. A research assistant or another anesthesia provider will be in the room to capture all data points. OLP will be measured immediately after insertion. This will be accomplished by closing the expiratory valve while keeping fresh gas flow at 3 liters/minute until equilibrium is reached.

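### Optional improvement: for sparse two-category secondary outcomes, Boschloo's exact test would recover some of the power that Fisher's exact test gives up, at an error rate still within 5%

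*Combined protocol and SAP*

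**What the plan says.** Section 15.3 compares categorical variables by "chi-squared or Fisher's exact tests to compare categorical variables between groups". It does not say when each is used, and states no significance level or sidedness.

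The secondary endpoints in section 3.2 include two with two categories: first-attempt success, listed in "first attempt success rate, ease of insertion, number of mid case adjustments", and "blood staining of LMA". No expected rate or power is given for either. The primary endpoint is "OLP immediately after placement", which is continuous, and the sample size in 15.2 was set on it alone, "to detect a difference of at least 3 cmH₂O in OLP between AuraGel and i-gel".

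Section 23.1 states: "We plan to enroll 148 patients and consent 165, assuming around 10% drop out". Section 5.1 randomizes 1:1 in permuted blocks, "to ensure approximate balance at any point in the study between the two groups". For complications, section 17.2 mentions a regression and a possible chi-square analysis, and names R or SAS as the software.

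**The concern.** Fisher's test conditions on both margins of the 2×2 table. When events are few, only a handful of tables are possible, and the attainable error rate can fall far below the nominal 5%. Boschloo's test uses the Fisher p-value as its statistic and sets the cutoff so that the maximum rejection probability over all common event rates stays within 5%. It therefore rejects whenever Fisher's test does, and sometimes when Fisher's does not.

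Blood staining and first-attempt failure are outcomes on which two airway devices could plausibly differ, and enrolment was not sized for them. If events are rare, the choice of exact test is one of the few ways left to gain power. The point concerns two-category outcomes only, not ordered ones such as ease of insertion.

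**Working it through.** **Inputs from the plan.** 148 enrolled 1:1, so 74 per arm if exactly balanced; 165 consented. **Assumed, because the plan gives none:** two-sided 5%; event rates of 1-3% v 6-12%, with 5% v 15% as a check; an exact test when the smallest expected count is below 5, otherwise uncorrected chi-squared.

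**Step 1, the plan's own figure.** The 148 rests on "estimated SD of 4.00 for AuraGel and 8.20 for i-gel", 80% power and a 3 cmH₂O difference. The normal approximation gives n per arm = (1.960 + 0.842)² × (4.00² + 8.20²) / 3² = 7.85 × 83.24 / 9 = 72.6, so 73 per arm and 146 in total. The noncentral t gives 148, and matches all four rows of the table at two-sided 5%, which supports that assumed level. Dropout: 148 / 0.90 = 164.4, so 165.

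**Step 2, when the fallback applies.** With equal arms and m events in total, the smallest expected count is m × 74/148 = m/2. It is below 5 when m < 10. At an assumed overall rate of 5%, P(m ≤ 9 | n = 148) = 0.79.

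**Step 3, true error at 74 v 74.** All 75 × 75 tables were enumerated as two independent binomials with a common rate. Boschloo's test rejects when the Fisher p-value is at most 0.0665.

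| Common rate | Fisher | Boschloo |
|---|---|---|
| 2% | 0.17% | 0.79% |
| 3% | 0.59% | 1.85% |
| 5% | 1.47% | 3.18% |
| Maximum over all rates | 3.95% | 4.89% |

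The combined rule (chi-squared, else exact test) has a maximum of 5.83% with either fallback, set by chi-squared at a common rate of 50%. At a common rate of 7%, changing the fallback moves the combined rule from 4.31% to 5.07%.

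**Step 4, power of the combined rule at 74 v 74.**

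| Rates | Fisher fallback | Boschloo fallback | Gain (points) |
|---|---|---|---|
| 1% v 6% | 17.2% | 28.4% | 11.2 |
| 1% v 8% | 37.9% | 50.9% | 13.0 |
| 1% v 10% | 59.4% | 70.3% | 10.9 |
| 2% v 8% | 27.3% | 35.9% | 8.6 |
| 2% v 10% | 47.3% | 55.1% | 7.8 |
| 3% v 12% | 54.4% | 58.0% | 3.6 |
| 5% v 15% | 54.2% | 54.8% | 0.6 |

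**Step 5, other arm sizes.** Gains of the combined rule over the first six rate pairs:
- 73 v 75: 0.6 to 8.5 points with the higher rate in the larger arm, 4.1 to 9.8 with it in the smaller arm.
- 72 v 76: about 0.6 to 14, depending on direction.
- 70 v 78: 0 with the higher rate in the larger arm, 2.4 to 6 with it in the smaller arm.
- 82 v 82: 0.3 to 7.9.
- 82 v 83 (all 165 analysed): 0 in one direction, about 1 to 4 in the other.

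**Step 6, single tables.** For 5 v 0 at 74 v 74, Fisher's p = 2 × (74·73·72·71·70)/(148·147·146·145·144) = 0.058; Boschloo's p is about 0.040. For 7 v 1 the values are 0.063 and 0.044.

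**The case against.** The strongest reply is that nothing here is an error. Fisher's test controls type I error, the outcomes are secondary, and the expected-count rule and every event rate were supplied from outside the plan. All of that stands, and it limits the point to an optional efficiency gain.

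Three stronger readings are tempting, and the documents support none of them.

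- A reader might infer that the plan forfeits 8 to 13 points of power in general. Even at 74 v 74 the 3% v 12% case gains about 4, and 5% v 15% gains less than 1. The plan promises only approximate balance and expects about 10% dropout, so an exact 74 v 74 split is not assured, and step 5 shows how much the gain depends on it.
- A reader might infer that the change leaves the maximum false-positive rate untouched. That is true only of the combined rule. The exact test's own maximum rises from 3.95% to 4.89%, which is within 5% but is a rise. Nor does the combined rule itself hold 5%, with either fallback.
- A reader might infer that a 5 v 0 or 7 v 1 split would be non-significant only because of Fisher's test. At 73 v 75 with the events mainly in the smaller arm, Fisher's test already gives 0.027 and 0.032. With 7 in the larger arm, neither test rejects.

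It is also fair to say that sparse secondary outcomes are better read from estimates and intervals than from a p-value that moves from 0.058 to 0.040. That supports reporting the risk difference. It does not defeat choosing the better test, because Boschloo's is never less powerful than Fisher's.

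**Conclusion.** The point holds as an optional, cheap improvement for first-attempt success, blood staining and complications. At an assumed two-sided 5% level with 74 per arm, Fisher's test runs at about 0.2% to 1.5% true error for common rates of 2% to 5%. Under the assumed expected-count rule, a Boschloo fallback adds about 4 to 13 points for rates of 1-3% v 6-12%. With slightly unequal or larger arms the range is about 0 to 14, and once events are common enough for chi-squared almost nothing is gained. The exact test's own error stays at or below 5%. Power after the change is still only about 28% to 70% in the six sparse examples at 74 v 74, so a non-significant result would remain weak evidence of no difference.

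**What to change.** In section 15.3, for two-category outcomes, replace Fisher's exact test with Boschloo's exact test when any expected count is below 5, and keep chi-squared otherwise. Writing this also supplies the missing rule for choosing the test; the significance level and sidedness should be stated with it. Report the risk difference with its 95% confidence interval for each such outcome, and apply the same rule to the complications in section 17.2.

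The cost is one phrase in the plan and one line of code in R, which section 17.2 already names. No extra patients or data are needed. The downside is that clinical readers know Boschloo's test less well than Fisher's, so the report would need a sentence of explanation.

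### Section 15.3 names no test for ordered categories, so ease of insertion, if graded on three or more levels, would go to a test that ignores the order

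*Combined protocol and SAP*

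**What the plan says.** Section 15.3 sorts variables into two classes. For the first: "Univariate comparisons between groups will use t-tests or Mann-Whitney U-tests, as appropriate for normality, to compare continuous variables". For the second: "chi-squared or Fisher's exact tests to compare categorical variables between groups". It mentions neither ordered categories nor counts.

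Section 3.2 lists among the secondary outcomes "Time to placement, insertion attempts, first attempt success rate, ease of insertion, number of mid case adjustments". Section 6.2 lists the data to be collected, including "time to place LMA, number of attempts, ease of LMA insertion, blood staining". Neither section, nor the procedures in 5.1 and 5.2, defines a scale for ease of insertion or its number of levels. No section says whether ease, attempts or mid-case adjustments are to be treated as continuous or categorical.

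**The concern.** Ease of insertion has a natural order. If it is graded, the only class in 15.3 that fits is categorical, and that leads to chi-squared or Fisher's exact. Both give the same p-value however the grades are rearranged. They spread their sensitivity over every possible pattern of difference, while the question is directional: is one device easier to insert than the other?

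At stake is power for a secondary comparison in a trial sized on OLP alone, so there is no planned reserve for it. For attempts the difficulty is different. The choice between an ordered and an unordered test is not made in advance and could be made after the data are seen.

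**Working it through.** **Inputs from the documents.** Section 23.1: "We plan to enroll 148 patients and consent 165, assuming around 10% drop out". Section 5.1: "Once enrolled patients will be randomized 1:1 between the groups". That gives 74 per arm. Section 15.2 sizes the trial to "detect a difference of at least 3" cmH₂O in OLP, with SDs of 4.00 and 8.20 at 80% power.

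**Inputs that must be assumed.** Alpha is not stated; two-sided 0.05 is assumed. The number of ease levels (3 to 5), the grade percentages and the odds ratios are also assumptions.

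**Reproducing the plan's own figure.** Common SD = √((4.00² + 8.20²)/2) = √41.62 = 6.45. The normal approximation gives 2 × 7.85 × 41.62/9 = 72.6, so 73 per arm or 146 in total. The noncentral t calculation gives 148, and it matches all four table entries (56, 148, 74, 198). So two-sided 0.05 is consistent with the plan. For dropout, 148/0.90 = 164.4, rounded up to 165.

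**Ordered versus unordered test, analytic.** An ordered test puts the whole shift on 1 degree of freedom. For 80% power its noncentrality is λ = (1.960 + 0.842)² = 7.85. Pearson's test on k levels spreads the same λ over k − 1 degrees of freedom, so its power is P(χ²(k−1, λ) > the 95% point of χ²(k−1)).

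| Levels | df | Ordered test | Chi-squared | Loss (points) |
|---|---|---|---|---|
| 2 | 1 | 80% | 80% | 0 |
| 3 | 2 | 80% | 70.9% | 9.1 |
| 4 | 3 | 80% | 64.5% | 15.5 |
| 5 | 4 | 80% | 59.5% | 20.5 |

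**Simulation for a 4-level ease scale.** 74 per arm, tie-corrected Mann-Whitney against Pearson chi-squared, one arm at an assumed 60/25/10/5% from easiest to hardest, common odds ratio 2.5. The direction matters. The odds of the easiest grade are 0.60/0.40 = 1.5.

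- Shift toward easier: odds 1.5 × 2.5 = 3.75, so 79% in the easiest grade. Power is 71% (Mann-Whitney) against 53% (chi-squared).
- Shift toward harder: odds 1.5/2.5 = 0.6, so 37.5% in the easiest grade. Power is 84% against 70%.
- With no difference, both tests reject in about 4 to 5% of trials, so the gain is not bought with type I error.

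**Simulation for attempts, if treated as categorical.** Assumed 85/12/3% for one, two and three attempts, shifted toward more attempts:

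| Odds ratio | Mann-Whitney | Chi-squared | Loss (points) |
|---|---|---|---|
| 2 | 38.9% | 29.3% | 9.7 |
| 2.5 | 63.7% | 52.4% | 11.3 |
| 3 | 80.5% | 71.0% | 9.6 |

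Losses are taken before rounding. Over both directions the loss is about 7 to 12 points at these odds ratios.

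**Sensitivity.** Over the 3-to-5-level scenarios examined, with odds ratios from 1.5 to 4, the loss runs from about 1 to 23 points. It is small when both tests have very low or very high power. When the difference is not a consistent shift, the ranking can reverse: 60/30/10% against 60/20/20% gives 41.9% (chi-squared) against 7.9% (Mann-Whitney), and 70/20/10% against 50/40/10% gives 68.6% against 57.9%.

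**The case against.** The strongest reply is that the plan does not assign these outcomes to chi-squared. A reader might infer from 15.3 that every insertion outcome goes to an unordered test. The text does not say so. Attempts and mid-case adjustments are counts. Treated as numeric, they reach Mann-Whitney through the plan's own normality rule. Ease could be recorded as easy/difficult, which loses nothing, or on a numeric rating like the 0–10 sore-throat score, which could also go to Mann-Whitney. This stands. The loss needs two conditions that the documents do not supply: a scale with three or more grades, and analysis as unordered categories.

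Three further points stand in part.

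- **Direction of effect.** Section 15.3 summarises categorical data by count and percent, so a reader could see which device did better. What is missing is an effect estimate with an interval, and 15.3 names none for any comparison between groups.
- **Attempts.** First-attempt success is already a separate outcome and captures most of the information. At an assumed 85/12/3%, chi-squared on one versus more than one attempt has 39.1% power at odds ratio 2 and 81.2% at 3, about the same as Mann-Whitney on the full count (38.9% and 81.3% in the same run).
- **Cost of switching.** An ordered test is not better against every alternative, as the non-shift patterns show, and the odds ratio brings in the proportional-odds assumption.

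None of this removes the gap. A graded ease outcome has no suitable rule in 15.3, because Mann-Whitney is named there for continuous variables only.

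**Conclusion.** The point holds as a conditional one of low severity. If ease of insertion has three or more grades, 15.3 as written sends it to a test that ignores their order. With two-sided 0.05, a consistent shift and 80% power for an ordered test, the loss is about 9, 15 and 20 points at 3, 4 and 5 levels. At two levels it is zero. For attempts the test is unspecified, not wrong; if attempts are treated as categorical with the assumed distribution, the loss is about 7 to 12 points at odds ratios 2 to 3.

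A reader might take 9 to 20 points as a fixed property of this trial. It is not, since the number of levels, the effect and alpha are all assumed. Nor do the documents support reading this as a threat to the main result. These are secondary outcomes with no stated power target, and the OLP analysis and the sample size of 148 do not change.

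**What to change.** In section 15.3, state that ease of insertion (if graded) and number of attempts will be compared with the tie-corrected Mann-Whitney test and reported with a proportional-odds odds ratio and 95% CI. Keep chi-squared or Fisher's exact for yes/no outcomes such as first-attempt success and blood staining. Define the ease scale at the same time, in 3.2 or 5.2, so that it is clear which rule applies.

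The cost is a sentence or two, with no new data and no extra patients. The downside is small: less power than chi-squared if the devices differ in a pattern that is not a consistent shift, and an odds ratio that rests on proportional odds. The counts and percentages by grade, already planned, would let a reader see either problem.
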